7.2.3.1 Hematology

Hematology tests include a complete blood count (CBC): a total white blood cell count (WBC), differential count, red blood cell count (RBC), hemoglobin (Hb), hematocrit and a platelet count.

[figure not shown]
Hematological tests will be performed at screening, on Day 1 (repeated prior to administration of the study drug, if performed more than 7 days prior to Day 1), Week 4, Week 10, Week 20, Week 30, Week 40, and Week 50 or End of treatment visit.

In the event of Grade 2, Grade 3 or Grade 4 hematological toxicities that require study drug dose modifications or interruptions, hematological tests should be repeated weekly until recovery to the baseline value or Grade 1.

7.2.3.2 Blood chemistry

Serum chemistry tests should include urea/BUN, creatinine, LDH, total protein, electrolytes (sodium, potassium and calcium), total bilirubin, GGT, albumin, alkaline phosphatase, AST/SGOT, ALT/SGPT, uric acid and fasting glucose. Patients should fast for 12 hours prior to blood sampling.

Serum chemistry should be performed at screening, on Day 1 (repeated prior to administration of the study drug, if performed more than 7 days prior to Day 1), Week 4, Week 10, Week 20, Week 30, Week 40, and Week 50 or End of treatment visit.

In the event of Grade 2, Grade 3 or Grade 4 non-hematological toxicities that require study drug dose modifications or interruptions, biochemistry tests should be repeated weekly until recovery to the baseline value or Grade 1.

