The most common adverse events (AEs) suspected to be related to treatment from the pooled of safety data were (in decreasing order), with an incidence $\geq 10\%$, reported in association with everolimus plus exemestane therapy (see Table 1-1) were consistent with what was previously reported: stomatitis, rash, fatigue, decreased appetite, diarrhea, infections, dysgeusia, nausea, pneumonitis, weight decreased, anemia, epistaxis, hyperglycemia, thrombocytopenia, pruritus, asthenia, peripheral edema, hypercholesterolemia, epistaxis and headache.

The most common grade 3/4 ADRs (incidence $\geq 1/100$ to $< 1/10$ and suspected to be related to treatment by the investigator) were stomatitis, anemia, hyperglycemia, infections, fatigue, infections, pneumonitis, diarrhea, asthenia, thrombocytopenia, neutropenia, dyspnea, lymphopenia, proteinuria, hemorrhage, hypophosphatemia, rash, hypertension, aspartate aminotransferase (AST) increased, and alanine aminotransferase (ALT) increased, and pneumonia.

Further details related to everolimus safety can be found in the everolimus [Investigator's Brochure].

In clinical trials and post-marketing spontaneous reports, everolimus has been associated with serious cases of the following:

- hepatitis B reactivation, including fatal outcome. Reactivation of infections is an expected event during periods of immunosuppression.
- renal failure events (including fatal ones) and proteinuria. Monitoring of renal function is recommended.
- amenorrhea (including secondary amenorrhea).

- pneumocystis jirovecii pneumonia (PJP), some with a fatal outcome.
- angioedema has been reported with and without concomitant use of everolimus mTOR and ACE inhibitors.

Table 1-1 Study Y2301 (BOLERO-2): Most common Adverse Events (equal or greater than 10% of patients)

AE preferred term	Everolimus + Exemestane (n=482), %					Placebo + Exemestane (n=238), %				
	All	1	2	3	4	All	1	2	3	4
Stomatitis	59	29	22	8	0	12	9	2	1	0
Rash	39	29	9	1	0	7	5	2	0	0
Fatigue	37	18	14	4	< 1	27	16	10	1	0
Diarrhea	34	26	6	2	< 1	19	14	4	1	0
Nausea	31	21	9	< 1	< 1	29	21	7	1	0
Decreased appetite	31	19	10	2	0	13	8	4	1	0
Weight decreased	28	10	16	2	0	7	3	5	0	0
Cough	26	21	4	1	0	12	8	3	0	0
Dysgeusia	22	18	4	0	0	6	6	0	0	0
Dyspnea	22	10	6	5	< 1	11	8	2	1	< 1
Headache	23	17	6	< 1	0	15	13	2	0	0
Arthralgia	21	15	5	1	0	17	11	6	< 1	0
Peripheral edema	21	14	6	1	0	6	5	1	< 1	0
Anemia	21	4	10	7	1	5	2	2	< 1	< 1
Back pain	15	10	5	< 1	0	11	6	3	2	0
Epistaxis	17	16	2	0	0	1	1	0	0	0

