7.2.3.4 Other laboratory tests

Coagulation assessments such as international normalized ratio (INR) or activated partial thromboplastin time (aPTT) should be performed at screening/baseline and repeated if clinically indicated.

A urinalysis assessment according to local routine will be performed only at screening/baseline.

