8.1.3 Adverse events of special interest

The adverse events of special interest associated with mTOR inhibition include:

- Stomatitis
- Non-infectious pneumonitis
- Infections
- Hyperglycemia
- Hyperlipidemia
- Hypophosphatemia
- Skin Rash
- Hypersensitivity
- Wound healing complications
- Increased creatinine/renal failure/proteinuria
- Cardiac failure

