Table 6.12.2 Treatment-Emergent Adverse Events of Special Interest by CTCAE Grade of Non-Asian Patients - Safety Set

Table 6.13 Treatment-Emergent Adverse Event of Special Interest Associated with mTOR Inhibition, any CTCAE Grade Overall and in Asian Subgroup - Safety Set

	Asian (N=xx)		Non-Asian (N=xx)		Total (N=xxx)	
	Patients	Events	Patients	Events	Patients	Events
Any TEAE	xx (xx.x)	xx	xx (xx.x)	xx	xx (xx.x)	xx
Stomatitis	xx (xx.x)	xx	xx (xx.x)	xx	xx (xx.x)	xx
Non-infectious pneumonitis	xx (xx.x)	xx	xx (xx.x)	xx	xx (xx.x)	xx
Infection (including pneumonia)	xx (xx.x)	xx	xx (xx.x)	xx	xx (xx.x)	xx
Hyperglycaemia	xx (xx.x)	xx	xx (xx.x)	xx	xx (xx.x)	xx
Hyperlipidaemia	xx (xx.x)	xx	xx (xx.x)	xx	xx (xx.x)	xx
Hypophosphataemia	xx (xx.x)	xx	xx (xx.x)	xx	xx (xx.x)	xx
Rash	xx (xx.x)	xx	xx (xx.x)	xx	xx (xx.x)	xx
Hypersensitivity	xx (xx.x)	xx	xx (xx.x)	xx	xx (xx.x)	xx
Increased creatinine/renal failure/proteinuria	xx (xx.x)	xx	xx (xx.x)	xx	xx (xx.x)	xx
Cardiac failure congestive	xx (xx.x)	xx	xx (xx.x)	xx	xx (xx.x)	xx

Asian: Indonesia, India, Vietnam, Turkey, South Korea, Thailand, Malaysia, Taiwan or Jordan.

Non-Asian: Australia, Morocco, South Africa or Tunisia.

TEAE: Treatment emergent adverse event. TEAE are defined as any adverse event with a start date on or after the date of the first dose of study drug and within 30 days of treatment discontinuation.

Note: All percentages (%) are presented with a denominator of the total number of patients in the safety set.

The following tables will follow the format of Table 6.13:

Table 6.13A Treatment-Emergent Adverse Event of Special Interest Associated with mTOR Inhibition, CTCAE Grade 1 Overall and in Asian Subgroup –Safety Set

Table 6.13B Treatment-Emergent Adverse Event of Special Interest Associated with mTOR Inhibition, CTCAE Grade 2 Overall and in Asian Subgroup –Safety Set

Table 6.13C Treatment-Emergent Adverse Event of Special Interest Associated with mTOR Inhibition, CTCAE Grade 3 or 4 Overall and in Asian Subgroup –Safety Set

Table 6.13D Treatment-Emergent Adverse Event of Special Interest Associated with mTOR Inhibition, CTCAE Grade 3 Overall and in Asian Subgroup –Safety Set

Table 6.13E Treatment-Emergent Adverse Event of Special Interest Associated with mTOR Inhibition, CTCAE Grade 4 Overall and in Asian Subgroup –Safety Set

Table 6.14 Time to Resolution of Treatment-Emergent Adverse Event of Special Interest Associated with mTOR Inhibition, Grade 3-4 - Safety Set

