Baseline is defined as the last non-missing value prior to the first study drug dose.

Baseline percentage is based on N. Percentage for worst post-baseline value is based on Baseline n.

Table 10.2.7 Hematology shift table based on normal range for parameters with no defined CTC grade for Non-Asian Patients- Safety Set

Non-Asian: Australia, Morocco, South Africa or Tunisia.

Low/High categories defined by normal ranges

Only the hematology parameters without CTC grades are included

Baseline is defined as the last non-missing value prior to the first study drug dose.

Baseline percentage is based on N. Percentage for worst post-baseline value is based on Baseline n.

Table 10.3.1 Blood Chemistry: Observed and Change from Baseline Overall and in Asian Subgroup - Safety Set

Laboratory Test/ Visit	Statistic	Asian (N=xx)	Non-Asian (N=xx)	Total (N=xxx)
Blood Urea Nitrogen (BUN):				
Baseline (BL)	n	xx	xx	xx
	Mean (SD)	xx (xx.x)	xx (xx.x)	xx (xx.x)
	Median	xx	xx	xx
	Min, Max	(xx.x, xx.x)	(xx.x, xx.x)	(xx.x, xx.x)
Week 4 Change from BL	n	xx	xx	xx
	Mean (SD)	xx (xx.x)	xx (xx.x)	xx (xx.x)
	Median	xx	xx	xx
	Min, Max	(xx.x, xx.x)	(xx.x, xx.x)	(xx.x, xx.x)
Week 10 Change from BL	n	xx	xx	xx
	Mean (SD)	xx (xx.x)	xx (xx.x)	xx (xx.x)
	Median	xx	xx	xx
	Min, Max	(xx.x, xx.x)	(xx.x, xx.x)	(xx.x, xx.x)
Include "Week X Change from BL" where X= 20, 30, 40, 50, Etc.	:			
End of Treatment Change from BL	n	xx	xx	xx
	Mean (SD)	xx (xx.x)	xx (xx.x)	xx (xx.x)
	Median	xx	xx	xx
	Min, Max	(xx.x, xx.x)	(xx.x, xx.x)	(xx.x, xx.x)
Repeat for other laboratory tests: Creatinine, Sodium, Fasting Glucose, Potassium, Uric acid, Calcium, LDH, Total protein, Albumin, SGOT (AST), SGPT (ALT), Alkaline phosphatase, GGT, Total bilirubin, Urea				

Asian: Indonesia, India, Vietnam, Turkey, South Korea, Thailand, Malaysia, Taiwan or Jordan.

Non-Asian: Australia, Morocco, South Africa or Tunisia.

SD: Standard Deviation.

Table 10.3.2 Biochemistry shift table based on CTC grade - Safety Set

Parameter	Baseline n (%)	Everolimus + Exemestane (N=xxx)					
		Worst post-baseline value					
		Grade 0 n (%)	Grade 1 n (%)	Grade 2 n (%)	Grade 3 n (%)	Grade 4 n (%)	Missing n (%)
Parameter 1							
Grade 0	xx (xx.x)	xx (xx.x)	xx (xx.x)	xx (xx.x)	xx (xx.x)	xx (xx.x)	xx (xx.x)
Grade 1	xx (xx.x)	xx (xx.x)	xx (xx.x)	xx (xx.x)	xx (xx.x)	xx (xx.x)	xx (xx.x)
Grade 2	xx (xx.x)	xx (xx.x)	xx (xx.x)	xx (xx.x)	xx (xx.x)	xx (xx.x)	xx (xx.x)

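### Hypophosphatemia and proteinuria are prespecified adverse events of special interest, but no serum phosphate is scheduled at any visit and no urinalysis on treatment, so their incidences in SAP Table 6.13 are liable to be under-reported by an unknown amount

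*Protocol*

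**What the plan says.** Protocol Section 8.1.3 opens its list with "The adverse events of special interest associated with mTOR inhibition include" and includes "Hypophosphatemia" and "Increased creatinine/renal failure/proteinuria". SAP Table 6.13 has a row for "Hypophosphataemia" and one for the renal composite. Its note makes the full Safety Set the denominator for every percentage.

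The laboratory schedule is as follows.

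- **Chemistry.** Section 7.2.3.2: "Serum chemistry tests should include urea/BUN, creatinine, LDH, total protein, electrolytes (sodium, potassium and calcium), total bilirubin", then liver enzymes, albumin, uric acid and fasting glucose. Footnote 5 of Table 7-1 says electrolytes without naming them. SAP Table 10.3.1 starts with BUN and continues "Repeat for other laboratory tests: Creatinine, Sodium, Fasting Glucose, Potassium, Uric acid, Calcium, LDH, Total protein, Albumin", followed by liver tests and urea. Listings 18.2.1 and 18.2.2 match it. Phosphate is in none of these (alkaline phosphatase is a different test).
- **Urine.** Section 7.2.3.4: "A urinalysis assessment according to local routine will be performed only at screening/baseline". Table 7-1 marks urinalysis at screening and leaves later testing to clinical indication.

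The background section names both events among the most common grade 3/4 drug reactions, in the class from 1/100 to below 1/10: "neutropenia, dyspnea, lymphopenia, proteinuria, hemorrhage, hypophosphatemia, rash, hypertension".

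**The concern.** Section 10.5 rests the primary safety assessment mainly on adverse event frequency, including laboratory values that qualify as adverse events. A value that is never measured cannot qualify. Both abnormalities are found by a laboratory test, and the plan leaves that test to local routine or clinical suspicion.

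If untested patients count as event-free, a low figure in Table 6.13 cannot be told apart from little testing. Because testing is local and the Asian and Non-Asian columns are defined by country, a difference between columns could also reflect how often sites test. A reader would take these rows as incidences in the treated population, which the design does not support.

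**Working it through.** **The plan's own figure.** There is none to reproduce. Section 10.7 describes a descriptive study of up to 400 patients with no hypothesis testing, and no detection rate is stated.

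**Step 1: set the laboratory-defined events against the scheduled tests.**

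| Event of special interest | Test | On-treatment schedule |
|---|---|---|
| Hyperglycemia | Fasting glucose | Day 1, Weeks 4, 10, 20, 30, 40, 50/EOT (7.2.3.2) |
| Hyperlipidemia | Cholesterol, triglycerides | Same visits (7.2.3.3; Table 7-1 footnote 5) |
| Increased creatinine/renal failure | Creatinine, urea/BUN | Same visits (7.2.3.2) |
| Hypophosphatemia | Serum phosphate | None; not at baseline either |
| Proteinuria | Urine protein | None (7.2.3.4), or on clinical indication (Table 7-1) |

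The first three are tested at every visit and the last two at none. The two urinalysis statements disagree with each other, but neither fixes an on-treatment test.

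**Step 2: what the denominator does.** Let N be the Safety Set, p the true incidence of reportable events and s the share of those that are detected and recorded. Expected recorded cases are N × p × s. Divided by N, the reported rate is p × s, so the shortfall is p × (1 − s). The documents give no s, so the direction is known but the size is not.

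**Step 3: the only frequency in the protocol.** The grade 3/4 class runs from 1% to below 10%. With N = 400 (the planned maximum), 0.01 × 400 = 4 and 0.10 × 400 = 40, the upper limit being excluded: 4 to fewer than 40 patients per event. This counts true cases under the class limits, not missed ones.

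**Step 4: illustration with assumed s.** Expected recorded cases, N = 400:

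| True p | s = 1 | s = 0.75 | s = 0.50 | s = 0.25 |
|---|---|---|---|---|
| 1% | 4 | 3 | 2 | 1 |
| 5% | 20 | 15 | 10 | 5 |
| 10% (excluded limit) | 40 | 30 | 20 | 10 |

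- At p = 5% and s = 0.50, 10/400 = 2.5%, with a Clopper-Pearson 95% interval of 1.21% to 4.55%. The interval excludes the true 5%, because it reflects sampling error and not missed detection.
- At p = 1% and s = 0.50, the chance of recording no case is (1 − 0.005)^400 ≈ 0.135.
- If two regions shared p = 5% but had s = 0.75 and s = 0.50, their expected rates would be 3.75% and 2.5% with no difference in toxicity.

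Every s here is assumed; none comes from the documents.

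**The case against.** The strongest reply is that the plan does not forbid these tests. Section 7.2.3.2 gives a minimum list. Section 7.2.3 allows tests as often as clinically needed, and Table 7-1 footnote 5 ties safety tests to routine practice. Section 8.1.1 names laboratory tests as one route by which adverse events are found. Cases can therefore be found and reported. This stands, and it rules out saying that phosphate is never measured or that cases surface only by chance. It does not replace scheduled ascertainment.

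The reply also limits the point in these ways.

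- **Reportability.** Sections 7.2.3 and 8.1.1 make a laboratory abnormality an adverse event only if it is clinically significant, symptomatic, or needs therapy or a treatment change. Some mild silent abnormalities would not be reported even if measured. Section 3.1.1 also does not list urinalysis among the laboratory results in the primary endpoint, so proteinuria enters only through adverse event incidence.
- **Composite row.** A reader might infer that Table 6.13 hides proteinuria behind creatinine and renal failure. It does not: SAP Tables 6.11 and 6.2.1 show recorded events by preferred term, and scheduled creatinine partly covers the composite.
- **Frequency.** A reader might take 40 of 400 as the expected number. The class excludes 10%, and neither event appears in protocol Table 1-1, which lists adverse events of any grade in at least 10% of patients in the registration trial. The upper end should not be expected.
- **Data route.** Sections 7.1 and 7.2.3 keep laboratory values in source documents and out of the CRF, while the SAP tabulates them. A count of patients tested may therefore not be in the database.

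**Conclusion.** The point holds as a gap in ascertainment. Two prespecified events of special interest have no scheduled on-treatment test, while the other laboratory-defined ones are tested at each visit, and Table 6.13 treats untested patients as event-free. The two incidences are liable to be too low, by an amount that the documents do not allow anyone to calculate, and they may vary with local practice.

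A reader might go further and infer that the trial will under-report both events, that the rates will be near zero, or that the Asian and Non-Asian columns will differ for this reason. The documents support none of these. They give no detection rate and nothing on testing practice by country, and clinically triggered tests can still produce reported events. The range of 4 to fewer than 40 of 400 patients per event is a frequency class applied to the planned maximum, and the illustrative rates rest on assumed detection shares.

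The change is worth making because the rows belong to the primary safety output and the remedy is small.

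**What to change.** 1. **Phosphate.** Name it among the electrolytes in Section 7.2.3.2 and in footnote 5 of Table 7-1, run on the sample already drawn at each visit, with clinically significant values reported through the Adverse Events CRF. Add it to the SAP chemistry tables and Listings 18.2.1 and 18.2.2 only if laboratory values are in the database. Sections 7.1 and 7.2.3 conflict with those outputs and must be reconciled with them first.
2. **Urine.** Reconcile Section 7.2.3.4 with the urinalysis row of Table 7-1, and state whether urine protein is checked at existing visits.
3. **SAP Table 6.13.** Footnote the hypophosphataemia and renal/proteinuria rows: serum phosphate and on-treatment urine protein were not systematically tested, so these rates are not whole-population incidences. Proteinuria needs no new table.

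The cost is one analyte on existing blood, a urine test at existing visits if adopted, and possibly higher reported adverse event rates. Items 1 and 2 help only patients still on treatment or yet to be treated, and enrolment was to close by 31 October 2014 at the latest. Item 3 needs only SAP wording and applies whatever is decided on the others. A denominator of patients tested would need data that the protocol currently keeps out of the CRF, so it is not part of that wording change.

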7.2.3.3 Serum lipid profile

A serum lipid profile assessment should be performed at screening, on Day 1 (repeated prior to administration of the study drug, if performed more than 7 days prior to Day 1), Week 4, Week 10, Week 20, Week 30, Week 40, and Week 50 or End of treatment visit. Patients should fast for 12 hours prior to blood sampling.

In the event of Grade 2, Grade 3 or Grade 4 toxicities serum lipid tests should be repeated weekly until recovery to the baseline value or Grade 1.

7.2.3.4 Other laboratory tests

Coagulation assessments such as international normalized ratio (INR) or activated partial thromboplastin time (aPTT) should be performed at screening/baseline and repeated if clinically indicated.

A urinalysis assessment according to local routine will be performed only at screening/baseline.

7.2.3.5 Hepatitis B viral load and markers, hepatitis C viral load

HBV-DNA, HBsAg, HBsAb, HBcAb and HCV-RNA will be measured at screening. Significant findings must be recorded as Relevant Medical History / Current Medical Conditions.

[figure not shown]
These assessments will be repeated every 3-6 weeks during the treatment period when required. Results will be recorded in the CRF. Hepatitis reactivation or flare will be managed according to guidelines presented in [Section 6.3.3](#), and will be recorded on the Adverse Events CRF.

7.2.3.6 ECG

A standard 12-lead ECG should be performed at screening/baseline. Tracings must be dated and signed by the investigator (or his/her designee) and filed with the patient's source documentation. Significant findings must be recorded as Relevant Medical History / Current Medical Conditions (if present before treatment). ECG may be repeated at the discretion of the investigator at any time during the study and as clinically indicated; any clinically relevant findings should be recorded on the Adverse Events CRF.

7.2.4 Pulmonary function tests (PFTs)

Pneumonitis is a known adverse event associated with the use of rapamycin and its analogues. Bronchoscopy with biopsy, broncho-alveolar lavage (BAL) and pulmonary function tests (PFTs) should be performed during the trial if clinically indicated and if warranted to exclude or manage non-infection pneumonitis. Significant findings must be recorded on the Adverse Events CRF.

7.3 Efficacy assessments

Tumor assessments are summarized in [Table 7-2](#).

Tumor response will be evaluated according to RECIST (Version 1.1) (See [Appendix 1](#)).

All patients should have at least one lesion that can be accurately measured in at least one dimension ≥ 20 mm with conventional imaging techniques or ≥ 10 mm with spiral CT as per RECIST 1.1 criteria, or in the absence of measurable disease have at least one lytic or mixed (lytic + blastic) bone lesion.

The same method of assessment and the same technique should be used to characterize each identified and reported lesion at baseline for each study tumor assessment after start of study treatment.

For patients with measurable disease at baseline, tumor progression will be evaluated at each assessment according to the RECIST 1.1 criteria (see [Appendix 1](#) for details). All patients being discontinued from the study for disease progression must have their progression documented using the RECIST 1.1 criteria.

A CT scan/MRI of the chest, abdomen and pelvis will be performed at screening and repeated at Week 10, Week 20, Week 30, Week 40, and Week 50/EOT. CT scan with contrast media should be used except for patients who are allergic/sensitive to the radiographic contrast media. Response will be assessed by local radiology review. The decision regarding patient management will remain with the local investigator. The same radiologist/physician should perform the evaluation for the entire duration of the study.

Bone scans/skeletal survey by X-ray must be performed at baseline within 6 weeks before enrolment. Positive areas on bone scans/X-ray must be assessed by MRI or CT scan with bone windows, prior to enrolment and should continue to be assessed using the same modality (MRI or CT scan) at Weeks 10, 20, 30, 40, and Week 50 or End of Treatment. Additional bone scans/X-ray should be performed if clinically indicated. Abnormalities found on subsequent bone scans/X-ray must be confirmed by MRI or CT scan.

In the absence of measurable disease at baseline, the following will be considered progression among patients with lytic or mixed (lytic + blastic) bone lesions:

- Appearance of one or more new lytic lesions in bone
- Appearance of one or more new lesions outside of bone
- Unequivocal progression of existing bone lesions.

Note: Pathologic fracture, new compression fracture, or complications of bone metastases will not be considered as evidence of disease progression, unless one of the above-mentioned criteria is fulfilled.

Table 7-2 Imaging collection plan

Procedure	Screening: Day -21 to -1	Treatment phase	End of treatment
CT or MRI (chest, abdomen, pelvis)	Mandated	Every 10 weeks from treatment start until progression or end of study	Mandated
CT or MRI for any site of disease	Mandated if suspected lesion at screening	If lesion at screening: every 10 weeks from treatment start until progression or end of study	Mandated if lesion at screening
Brain CT or MRI	Mandated at screening only if existing or suspected brain metastases	As clinically indicated	As clinically indicated
Bone scan/X-ray	Mandated	As clinically indicated	As clinically indicated
Bone CT or MRI	Mandated at screening only if skeletal abnormalities identified by bone scan/X-ray at screening	If bone lesion at screening: every 10 weeks from treatment start until progression or end of study	Mandated only if bone lesion at screening
Skin color photography	Mandated if skin lesions at screening	If skin lesions at screening: every 10 weeks from treatment start until progression or end of study	Mandated if skin lesions at screening

